10.1.4.1 ADAS-Cog (Word Recall, Delayed Recall, Orientation)

The ADAS-Cog administration will be restricted to the Word Recall and Orientation subtests, as these have demonstrated to have the greatest sensitivity to change in MCI [25]. For Word Recall, participants are given three trials to learn a list of 10 high-frequency, high imagery nouns presented one at a time in block letters on white cards. Immediate recall is assessed after each presentation trial. Delayed recall is assessed after approximately 5 minutes. Orientation for person, time and place is assessed with 10 examiner-administered questions.

10.1.4.2 Boston Naming Test (BNT) – 15-item

This is an abbreviated version of the Boston Naming Test and will be administered to assess visual confrontation naming [26]. Participants are asked to identify (i.e., name) line drawings of objects.

10.1.4.3 Brief Visuospatial Memory Test-Revised (BVMT-R)

On this task, participants are presented with a 2 x 3 array of six line drawings for ten seconds. After the display is taken away, participants are asked to draw each figure accurately and in its correct location on the page. There are three learning trials, a 25-minute delayed recall trial, a delayed recognition memory trial and a copy trial [27].

10.1.4.4 Craft Story 21 Immediate and Delayed Recall

This test assesses the ability to recall a story[28]. Participants are read a story and are immediately asked to recall what they can remember. After a 20-minute delay, participants are asked again to recall the story.

10.1.4.5 Digit Symbol Modalities Test-Oral Version

This is a timed task that gives participants 120 seconds to orally match geometric figures with specific numbers according to a defined key (specifying which symbols are assigned to which numbers) that is provided at the top of the stimulus page [29].

10.1.4.6 DKEFS Color-Word Interference Test (CWIT)

This timed task requires participants to (1) name a series of colors, (2) read a series of words and then (3) name the color of the ink of dissonant color words (i.e., must say “green” when the word red is written in green ink) [30]. The latter task is a measure of response inhibition as participants must inhibit an overlearned verbal response of reading the particular word (red) in favor of generating a conflicting response of naming the different ink color (green). For the fourth trial, participants must alternate between naming the ink color of dissonant color words and simply reading the word and ignoring the ink color (inhibition and switching). The score is total time it takes to complete each trial. The maximum time for the color naming and word reading trials is 90 seconds and the maximum time for the inhibition and inhibition switching trials is 180 seconds.

10.1.4.7 DKEFS Verbal Fluency

This verbal fluency test includes phonemic (letter) fluency, semantic (category) fluency and category switching [30]. For the phonemic fluency task, the participant is asked to generate words that begin with a particular letter as quickly as possible, within a 60 second time period. Three trials are given, each with a different letter. The semantic fluency task asks participants to verbally generate as many words as they can according to specific categories (animals and boys names) with a 60 second time period. The category switching task asks participants to alternate between saying words from two different semantic categories (fruits and furniture) with a 60 second time period.

10.1.4.8 Oral Trail Making Test

The oral version of the Trail Making Test provides an assessment of sequential set-shifting without the motor and visual demands of the written Trail Making Test [31]. For Part A, participants are asked to count from 1 to 25 as quickly as possible. For Part B, participants are asked to switch between number and letter in sequential order (e.g. 1-A, 2-B, 3-C) until the number 13 is reached. Scoring is the total time to complete each part.

10.1.5 *Cogniciti Brain Health Assessment*

The Cogniciti Brain Health Assessment (BHA) is a self-administered online assessment of memory and executive function, comprised of four cognitive tests [32]. The Cogniciti BHA also includes a demographic and health questionnaire. The four cognitive tests included in the Cogniciti BHA are:

- 1) **Spatial Working Memory** is a test of visuospatial working memory. This task requires participants to match several pairs of hidden shapes across three trials and to avoid unnecessarily returning to previously searched locations. Number of responses across three trials is measured.
- 2) **Stroop Interference** is a speeded test of response inhibition. Participants are required to identify the number of words shown on each trial. During interference trials, the number of words is incongruent with the meaning of the word (e.g. the word “two” is written one time). Median reaction time on incongruent trials is measured.
- 3) **Face-Name Association** is a test of associative recognition. The participant is shown various faces paired with names and then completes a recognition task. Recognition accuracy is measured.
- 4) **Number-Letter Alternation** is a test of alternating attention. Participants are required to alternate sequencing numbers and letters in ascending order as quickly as possible. Time to completion is measured.

10.1.6 “Burst” Cognitive Testing

Participants will undergo five intensive measurement bursts, spaced approximately three months apart, over 12 months (at Baseline, Months 3, 6, 9, and 12) using the MyCogHealth mobile application. Each measurement burst will involve two mobile assessments per day for seven consecutive days. Each assessment session will take approximately 5-10 minutes to complete, and will include the 3 cognitive tests included in the current MyCogHealth battery (i.e., Symbol Match, Dot Memory, and Trail-Making A and B), as well as several brief questions assessing state factors at the time of testing (e.g., mood, fatigue, subjective cognitive ability).

Cognitive Tasks

Each cognitive task in the mobile battery takes 1-2 minutes to complete, ensuring feasibility for use in intensive measurement studies that include multiple sessions within a day.

Symbol Match assesses attention and information processing speed. Participants are shown a row of three symbol pairs at the top of the screen, and are simultaneously presented with two symbol pairs at the bottom of the screen. Stimuli are presented until a response is provided. The task is to decide, as quickly as possible, which of the two pairs presented at the bottom of the screen matches one of the pairs at the top of the screen. Participants complete 12 trials of this task. The dependent variable is median response time of correct trials.

Dot Memory assesses visual short-term memory. Each trial consists of 3 phases: Encoding, distraction, and retrieval. During the encoding phase, the participant is asked to remember the locations of 3 red dots on a 5 x 5 grid. After a 3-second study period, the grid is removed and the distraction phase begins, during which the participant is required to locate and touch all the F's among an array of E's. After performing the distraction task for 8 seconds, an empty 5 x 5 grid reappears on the screen, and participants are prompted to recall the locations of the initially presented 3 dots. Participants complete 4 trials of this task (encoding, distractor, retrieval), with a 1-second delay between trials.

Digital Trail Making Test assesses complex attention/controlled sequential processing. It is a digital analogue of the classic neuropsychological task.

Survey

As part of each mobile assessment participants will be asked to complete a series of single-item questions that assess state factors that can affect cognition (e.g. mood, fatigue, physical activity, subjective cognitive ability).

10.2 Behavioral and Functional Measures

Participants will complete the following behavioral and functional measures remotely through the LORIS survey tool. Each survey form is generated with a unique URL. This survey link URL can be emailed directly to respondents for survey completion from home. Participants will be provided with contact information for site study staff for any questions, concerns or if they experience any technical difficulties with completing the assessments.

10.2.1 COVID-19 Impact Survey

This is a 14-item questionnaire developed by the National Alzheimer's Coordinating Center (NACC) to assess the impact that the COVID-19 pandemic has had on older adults. Questions include symptoms, testing, social isolation, loneliness and disruption to everyday life [33].

10.2.2 Generalized Anxiety Disorder 7-Item Scale (GAD-7)

Anxiety symptoms will be assessed with the GAD-7 [34]. The participant is asked how frequently they felt the way that is described in a given item over the last two weeks (choices are “Not at all sure”, “Several days”, “Over half the days” & “Nearly every day”). If any of the items are indicated to have been experienced several days or more, there is a follow-up question on how much difficulty this created in being able to work, take care of things at home, or get along with other people. The score is based on the frequency of each experienced item with “Not at all sure” =0 points, “Several days” =1 point, “Over half the days” =2 points, and “Nearly every day” =3 points. A score greater or equal to 10 suggests generalized anxiety.

10.2.3 Geriatric Depression Scale (GDS)

Depressive symptoms will be assessed with the 15-item Geriatric Depression Scale [35]. This is a 15-item scale of Yes/No questions where each point represents a depressive answer. A score over 10 suggests depression and a score over 15 suggests major depression.

10.2.4 Lawton Brody Instrumental Activities of Daily Living (IADL) Scale

This is a 10-15-minute scale that can be completed by self-report or by informant (if available) and captures functional ability on 8 instrumental activities of daily living (telephone use, shopping, food preparation, housekeeping, laundry, transportation, medication management, and ability to handle finances) [36]. Each activity has a series of levels of capability described, ranging from full capability to no capability. A total score out of 23 is derived from the levels of capability for each activity with a higher score representing better functional capacity.

10.2.5 *Mild Behavioral Impairment Checklist (MBI-C)*

The MBI-C is a 32-item scale that assesses severity of behavioral symptoms in 5 domains: impaired drive/motivation (apathy); emotional dysregulation (mood/anxiety symptoms); impulse dyscontrol (agitation/aggression/abnormal reinforcement and reward salience); social inappropriateness (impaired social cognition); and abnormal thoughts/perception (psychotic symptoms) [37]. The MBI-C will be completed by a study partner/informant (if available). The study partner will be asked to select “Yes” only to each behavior that has been present for at least 6 months and is a change from the participant’s longstanding behavior.

10.2.6 *Research Satisfaction Survey*

A brief Research Satisfaction Survey will be administered to the participant at Baseline, Month 6 and Month 12 to evaluate satisfaction with this study. The survey may reveal specific aspects of the study that participants dislike, which can inform efforts to improve the experience for participants in the future.

10.2.7 *Sleep Disorders Questionnaire*

This brief self-report questionnaire will be used to assess Sleep Apnea, REM Sleep Behaviour Disorder and Restless Leg Syndrome (RLS). Sleep Apnea will be assessed using questions from the Stop-Bang Questionnaire [38]. RBD will be assessed using a single question from the Mayo sleep questionnaire: “Have you ever been told, or suspected yourself, that you seem to ‘act out your dreams’ while asleep (for example, punching, flailing your arms in the air, making running movements, etc.)?”[39]. RLS will be assessed using the 8-item Cambridge Hopkins Questionnaire [40].

10.3 BHPRO Outcome Measures

The following assessments will be completed online directly through BHPRO. Participants will receive an e-mail notification to login into BHPRO to complete the following assessments.

10.3.1 *Alzheimer’s Disease Knowledge Scale (ADKS)*

The Alzheimer’s Disease Knowledge Scale is a 30-item, true/false scale that was designed to assess knowledge about Alzheimer’s disease among laypeople, patients, caregivers, and professionals. It covers risk factors, assessment and diagnosis, symptoms, course, life impact, caregiving, and treatment and management [41]. This scale will be completed online within BHPRO to measure changes in dementia literacy.

10.3.2 *The General Self-Efficacy Scale (GSE)*

Self-Efficacy is a concept that refers to one's global confidence in their ability to cope with demanding or novel situations. The General Self-Efficacy scale is a 10-item, 4-point scale which measures one's perceived competence in dealing with a range of stressful or challenging situations [42]. The scale will be completed online within BHPro.

10.3.3 ***Perceptions Regarding Investigational Screening for Memory in Primary Care (PRISM-PC)***

Sections B and D of the PRISM-PC questionnaire will be used to assess attitudes toward dementia and dementia screening and will be completed online within BHPro. The PRISM-PC questionnaire captures participants' acceptance, perceived harms, and perceived benefits of dementia screening [43].

10.3.4 ***System Usability Scale (SUS)***

The SUS [44] is a simple scale giving a global view of subjective assessments of usability. An adapted 11-item version of the SUS will be used to measure usability of BHPro.

10.3.5 ***Technology Acceptance Model Questionnaire***

A web-based adapted version of the Technology Acceptance Model Questionnaire [45] will be used to evaluate user acceptance of BHPro. Questions include attitude, perceived usefulness and perceived ease of use of the technology.

11.0 EARLY DISCONTINUATION PROCEDURES

Participants are free to withdraw from study participation at any time, for any reason, and without prejudice.

Study Discontinuation for an individual participant may occur in the following circumstances:

1. Withdrawal of informed consent by the participant. If a study partner withdraws his/her willingness to participate, attempts will be made to find a replacement. If a replacement study partner is not identified, the participant will continue to be followed in the study and assessments completed to the extent possible.
2. Adverse event or other significant medical condition which, in the opinion of the Investigator, render it necessary to remove the individual from study participation.
3. Any other occurrence that, in the Investigator's opinion, makes continued participation contrary to the participant's best interests.

If the site investigator or CCNA Co-Principal Investigator (Co-PI) leadership team discovers sufficient reasonable cause for the premature termination of the study, the terminating party will provide written notification documenting the reason for study termination. The appropriate regulatory agencies and IRB/REB must be notified.

12.0 ADVERSE EVENTS

An adverse event (AE) is any untoward medical occurrence in a participant that occurs from the time of the baseline visit and up to 30 days after study participation has ended. For the purposes of reporting on the CTU study, an AE is defined as any unfavourable or unintended sign (e.g., including an abnormal laboratory finding), symptom, or disease associated with study procedures that are both **non-serious and either temporally or causally related to study procedures**. Pre-existing conditions, which increase in frequency or severity or worsen in nature during, or as a consequence of, a study procedure, may also be considered an AE if it meets the definition of being both non-serious and related to a study procedure.

An AE **does not** include:

- Medical or surgical procedures (e.g., surgery, endoscopy, tooth extraction, transfusion). The condition that leads to the procedure is the AE.
- Situations where an untoward medical occurrence has not occurred (e.g., hospitalization for elective surgery, social and/or convenience admissions).
- Worsening of symptoms associated with expected decline in memory or an associated co-morbid condition and not related to a study procedure.
- Those medical or surgical adverse events that are not related to the study procedures

12.1 Evaluation and Reporting of Adverse Events

All AEs both non-serious and either temporally or causally related to study procedures (i.e., a new event or an exacerbation of a pre-existing condition) that occur from the baseline visit and up to 30 days after study participation has ended will be recorded as an AE in LORIS. Adverse events that occur prior to the baseline visit will be documented as medical history. The Investigator must follow all AEs until the AE resolves, or until the Investigator determines the event is chronic or clinically stable. If an AE remains unresolved at the conclusion of participation in the BHSP, the Investigator will make a clinical assessment to determine whether continued follow-up of the AE is warranted.

The Investigator should attempt to establish a diagnosis of the event based on signs, symptoms and/or other clinical information. In such cases, the diagnosis should be documented as the AE and not the individual signs/symptoms.

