5.5 Potential Risks and Benefits Associated with this Study

5.5.1 *Potential Risks*

Risks associated with study participation are minimal and include risks related to the process of undergoing neuropsychological and remote cognitive testing, which may lead to fatigue and/or frustration associated with participating in cognitively demanding testing. Questionnaires on mood and lifestyle risk may increase negative affect. There may be minimal discomfort or disruption of sleep with the application and removal of the actigraph device and EEG headband. There may be risks associated with a breach in confidentiality. Strict privacy and confidentiality procedures have been implemented (see section [5.4 Participant Confidentiality](#)) to minimize this risk to the extent possible.

5.5.2 **Potential Benefits**

Participants in this study may experience benefits from participating in a web-based educational program including increased knowledge and engagement regarding ways to promote their brain health, and possible positive reduction in their risk profiles, though such improvement cannot be predicted with any certainty. This study is expected to benefit the general community in the future by promoting public interest, literacy, and engagement in lifestyle interventions for brain health and dementia prevention through dissemination of BHPro to the broader public.

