8.1.2.2 Video-Conference Screening Procedures

The following procedures will be conducted remotely via secure video-conference technology during the screening period (Estimated Time to Complete: 3.0-3.5 hours). Screening procedures may be completed over multiple days as long as all procedures are completed within 21 days prior to the first scheduled baseline video-call visit. Procedures and instruments will be adapted for remote administration (see section [9.0](#) Study Procedure Descriptions and section [10.0](#) Study-Specific Instruments).

- Review of inclusion/exclusion criteria
- Consent for medical record review
- Documentation of demographics, medical history (including past medical procedures), medications
- Hearing and Vision assessment
- CAIDE Score (derived score based on self-report and/or medical record review)

- Clinical Dementia Rating (CDR; if a study partner is not available, the CDR score will be decided by site-level research team consensus based on all other available information and utilizing best clinical judgement.)
- Logical Memory 1 & 2 from Wechsler memory scale
- Montreal Cognitive Assessment (MoCA)
- Lawton Brody Instrumental Activities of Daily Living (IADL)
- Brief Remote Neurological Exam (completed by Site Principal Investigator or qualified medical professional)

8.1.2.3 Confirmation of Study Eligibility by Site Principal Investigator (or designated Co-Investigator)

Following completion of the screening assessments above, the Site Principal Investigator (or Co-Investigator) will be responsible for confirming participant diagnosis and eligibility to be enrolled in the study.

8.1.3 **Remote Baseline Visit (+/- 2 weeks)**

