participant's home. The at-home kit will include detailed instructions on how to collect the sample and a study team member will provide guidance to the participant on how to properly collect and ship the sample during the Baseline video-call visit. A total of 2 mls of saliva will be collected by passive drool in 1 tube. Participants will be instructed not to eat, drink, smoke, or chew gum for 30 minutes prior to giving the sample. The samples will be collected, handled, stored and shipped according to established standard operating procedures. Instructions for collection, handling and shipping of saliva samples for DNA testing will also be provided in the Study Procedures Manual.

De-identified samples will be sent to the Clinical Genomics Centre in the Mount Sinai Hospital, [name], Canada and will be processed under the guidance of [name]. Samples will be stored for the duration of the study and until all planned analyses are complete, after which they will be properly destroyed according to established lab procedures.

A Polygenic Hazard Score (PHS) will be derived from a planned panel of single nucleotide polymorphisms that describes age of onset and ADD risk [16]. Both raw and processed data will be posted to the LORIS server.

9.1.6 ***Remote Neurological Exam***

A brief neurological examination will be conducted during screening by the site principal investigator or a designated medically qualified professional. The examination will be completed by a telemedicine visit using secure PIPEDA compliant video-conference technology (e.g. Zoom). The exam will be conducted following guidance from the American Academy of Neurology (AAN) and the Telemedicine and COVID-19 Implementation Guide (<https://www.aan.com/siteassets/home-page/tools-and-resources/practicing-neurologist-administrators/telemedicine-and-remote-care/20-telemedicine-and-covid19-v103.pdf>) and will include assessment of mental status, language, calculations, memory, cranial nerves, gate, motor, sensory, and cerebellar function.

9.2 ***Online Cognitive Testing***

Participants will be asked to complete cognitive testing remotely throughout the duration of the study. Participants will be provided with detailed instructions on each remote assessment at the baseline video-conference with a study team member. The following online cognitive assessments will be completed (see Schedule of Events ([Appendix 2](#)) for timing of assessments):

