12.3 Collection and Reporting of Serious Adverse Events (SAEs)

All SAEs thought to be **unanticipated and related to study procedures** must be collected from the time of the baseline visit and up to 30 days after study participation has ended. SAEs will be promptly assessed by the Investigator and documented in LORIS as described below.

In order to meet the requirements for reporting as an SAE in LORIS, an event **must meet all three criteria** as defined below:

- 1) **Serious**
 - a. Untoward occurrence that results in death, is a life-threatening situation, requires inpatient hospitalization or prolongation of existing hospitalization, results in significant disability/incapacity or is a congenital anomaly
- 2) **Unanticipated**
 - a. An AE that is not identified in nature, severity, or frequency in the relevant safety documents(s) or is not identified as a possible risk in the study protocol or the informed consent form
- 3) **Related to study procedures** in the judgement of the Principal Investigator taking into account all aspects of the event

If the Investigator believes that an SAE is related to a study procedure, this should be specified in the narrative section of the SAE report.

SAEs meeting the above definition must be reported in LORIS **promptly, but no later than 10 business days** of the Investigator becoming aware of the event.

In addition, Investigators must report SAEs to their local IRB/REB according to local safety reporting guidelines for submission of SAEs.

SAE information including event term, start/stop dates, severity, relationship to study procedures, whether the event caused the participant to withdraw from the study, and outcome will be entered into LORIS as specified in the Study Procedures Manual.

If only limited information on the SAE is initially available, follow-up reporting is required. If an ongoing SAE changes in its intensity or relationship to study procedures or if new information becomes available, a follow-up SAE report should be entered into LORIS within 10 days of the Investigator becoming aware of the updated information using the same procedure used for the transmission of the initial SAE and the same event term should be used. All SAEs should be followed to resolution or stabilization. For any questions relating to SAEs, please contact the CCNA coordinating center via telephone or email at the number listed in the Study Procedures Manual.

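### The LORIS windows for AEs and SAEs open at the baseline visit, so events related to the consented screening procedures stay out of the study's AE/SAE record

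*Protocol*

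**What the plan says.** **Collection window.** Protocol 12.0 defines an AE as an untoward occurrence that "occurs from the time of the baseline visit and up to 30 days after study participation has ended", and limits it to non-serious events with a temporal or causal link to study procedures. Section 12.1 repeats the baseline start and then says: "Adverse events that occur prior to the baseline visit will be documented as medical history". Section 12.3 covers serious events judged to be both unexpected and procedure-related; for these it says that they "must be collected from the time of the baseline visit and up to 30 days after study participation has ended".

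**What comes before baseline.** Section 8.1.2 requires consent before any study activity. Section 8.1.2.2 then lists the video-conference screening procedures, estimated at 3.0-3.5 hours and to be completed "within 21 days prior to the first scheduled baseline video-call visit". They include the CDR, Logical Memory, MoCA, the Lawton Brody IADL scale and a brief remote neurological exam. Section 9.1.6 says that this exam "will include assessment of mental status, language, calculations, memory, cranial nerves, gate, motor, sensory, and cerebellar function".

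**Stated risk.** Section 5.5.1 describes the risks as minimal. The first it names are "risks related to the process of undergoing neuropsychological and remote cognitive testing, which may lead to fatigue and/or frustration".

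**Other relevant text.** Section 8.1.3.1 lets screening and baseline take place at one remote visit, provided that consent has been given and eligibility confirmed. Section 5.2 requires the investigator to notify the IRB/REB of serious adverse events at the site under local policy, and gives no start date. The SAP describes no AE or SAE summary.

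**The concern.** A baseline start would be natural if the aim were to capture effects of exposure to BHPro. Section 12 does not define its events that way: the test for an AE or an SAE is the relation to a study procedure. Study procedures begin at screening, under study consent, so the window leaves out part of the exposure that the definition is about.

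At stake is whether the safety record is complete for a fully remote assessment model whose feasibility the study is meant to inform. Medical history is also a weaker record. For an AE, 12.2 requires onset and resolution dates, severity, relationship to procedures, any withdrawal and outcome, and 12.1 requires follow-up until the event resolves or is stable. Section 9.1.2, on medical history, attaches none of these duties.

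**Working it through.** The plan states no figure to reproduce here, so the check compares the definition, the window and the visit schedule.

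1. **Definition against window.** 12.0 and 12.3 tie reportable events to study procedures. 12.0, 12.1 and 12.3 open collection at baseline. The three windows agree with one another, so the mismatch is between the window and the definition. A small slip shows it: 12.1 speaks of adverse events before baseline, although 12.0 admits none before that visit.

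2. **What lies outside.** An estimated 3.0-3.5 hours of procedures per participant, spread over up to 21 days before the first baseline call, all after consent.

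3. **Same procedure, different record.** The CDR, MoCA, IADL scale and neurological exam are repeated at Month 12 (8.1.8 and Appendix 2).

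| Event related to the procedure | At screening | At Month 12 |
|---|---|---|
| Non-serious | Medical history (12.1) | AE in LORIS (12.1, 12.2) |
| Serious and unanticipated | Outside the LORIS SAE window (12.3); IRB/REB route under local policy (5.2) | SAE in LORIS (12.3) |

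   Logical Memory is given only at screening, so no event related to it can enter the AE/SAE record unless the visits are combined and the event is counted as baseline.

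4. **Screen failures.** The SAP's Enrolled Sample (Section 4) is everyone who consented to screening. Those who fail screening have the procedures but no baseline visit, so the window never opens for them.

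5. **Shared visit.** Where 8.1.3.1 is used, the protocol does not say at which moment the baseline visit begins. Two sites could record the same event on the same day differently.

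6. **Does other text close the gap?** The worsening clause in 12.0 can make a pre-existing condition an AE if a later study procedure aggravates it. That captures the later worsening, not the screening event itself. Section 5.2 can carry a serious event to the IRB/REB but does not place it in LORIS.

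**The case against.** The strongest reply is that this is a deliberate and consistent choice in a low-risk educational study. Screening consists of interviews, questionnaires, cognitive tests and a remote exam. The documents call the risk minimal, most of these procedures recur inside the window, and safety is not among the outcomes in Section 4. All of that stands. It limits the weight of the point but does not reconcile the window with the definition.

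A reader might infer more than the documents support:

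- **That screening events are never counted or reported.** Non-serious events are still documented, as medical history. Section 5.2 covers serious events at the site with no baseline start, and 12.3 adds a duty to report SAEs to the local IRB/REB.
- **That serious pre-baseline events are sent to medical history.** That sentence stands in 12.1, which concerns non-serious AEs. Section 12.3 sets the LORIS window and does not say where an earlier serious event goes.
- **That planned AE/SAE tables will understate harm.** The SAP plans no such tables. What is incomplete is the LORIS record.
- **That about 30% of exposure is uncovered.** Screening is 3.0/(3.0 + 2.5 + 4.0) = 31.6% to 3.5/(3.5 + 3.0 + 5.0) = 30.4% of estimated video time at screening, baseline and Month 12. But BHPro adds about 45 x 40 min = 30 h. Five 7-day bursts add 35 x 5 min = 2.9 h to 35 x 2 x 10 min = 11.7 h, depending on whether the 5-10 minutes apply per day (8.1) or to each of two daily sessions (9.2.2). The share is then 3.0/42.4 = 7.1% to 3.5/53.2 = 6.6%, before any device wear is counted. Neither share measures harm.

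**Conclusion.** The point holds in a limited form. Read literally, Section 12 omits from the AE/SAE record any event related to 3.0-3.5 hours of consented screening procedures per participant, and every such event in a screen failure. It leaves the boundary undefined for a shared visit.

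The documents give no event rate, so the number of missed events cannot be derived. With risks described as minimal, a small number of mostly mild events is the reasonable assumption. A fall during the remote exam followed by admission is conceivable, but the documents report no such event. No efficacy estimate changes.

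The conclusion assumes that the Study Procedures Manual, which is not among the documents, does not set an earlier start. The change is worth making because it is cheap and makes Section 12 consistent with its own definition.

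**What to change.** In Protocol 12.0, 12.1 and 12.3, start collection of procedure-related AEs and SAEs at the first study procedure performed after informed consent, and state that this includes screen failures. The start phrase in 12.1 is worded slightly differently from the other two sections, so each needs its own edit.

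In 12.1, keep medical history for two groups: events that began before that first procedure, and pre-baseline events not related to a study procedure. Without the second group, an unrelated event between screening and baseline might be recorded nowhere, because 12.0 excludes unrelated events and the Month 6 review looks back only to baseline. With the new start, the shared-visit boundary no longer affects procedure-related events.

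Cross-refer 12.3 to the IRB/REB duty in 5.2. Confirm that screen failures have a LORIS ID, or provide an equivalent log: 5.4 assigns the ID at enrollment, while 8.1.2.3 confirms eligibility for enrollment only after screening.

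**Cost:** wording in three sections, a few more mild AE entries and possibly a minor LORIS set-up step for screen failures. Because only procedure-related events qualify, the added workload should be small.
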